2.0 OBJECTIVES

2.1 PRIMARY OBJECTIVES

Sub-Study 1 (home quarantined COVID-19 patients): Median time to release from quarantine by meeting the following criteria: 1) No fever for 72 hours without the use of fever-reducing medication 2) improvement in other symptoms and 3) 7 or 10 days have elapsed since the beginning of symptom onset, depending on CDC guidelines at the time. (Outcomes based on 7 and 10 days will be constructed for each subject.)

The first date of quarantine will be considered the date of SARS-CoV-2 nasopharyngeal swab test that confirmed positivity.

Sub-Study 3 Healthcare worker prophylaxis: Rate of COVID-19 infection at 2 months

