1.2 SECONDARY OBJECTIVES

Sub-Study 1: Rate of participant-reported secondary infection of housemates, rate of hospitalization, rate of treatment related adverse events

Sub-Study 3: rate of treatment related adverse events

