Anterior nares specimen: Participants will self-collect these samples on day 0 (start date for HCQ) before the HCQ is taken, Day 3, and day 7

The PATCH Trial

Foam swab provided: Puritan 6" Sterile Standard Foam Swab w/ Polystyrene Handle (SKU # 25-1506 1PF)

Collection instructions: Use a single foam swab for collecting specimens from both nares. Insert foam swab into 1 nostril straight back (not upwards). Once the swab is in place, rotate it in a circular motion 2 times and keep it in place for 15 seconds. Repeat this step for the second nostril using the same swab. Remove foam swab and insert the swab into the supplied tube.

Storage instructions: The collected swab should be placed into the bag marked "Nares swabs collected" and the date and time of the swab collection should be filled out Redcap. The "Collected" bag is then placed in the freezer in the same sealed container as the oral fluid.

Specimen stability for all specimen types for all tests is now as follows:

Room temperature: 5 days

Refrigerated (2 °C–8 °C): 5 days

Frozen (-20 °C): 7 days

Frozen (-70 °C): Acceptable

Specimen pickup: At the end of quarantine, or end of study procedures, the nares swabs will be collected. And shipped to Quest Diagnostics to assess viral titers. Cold packs or dry ice should be used during collection and cold packs should be used during shipping to Quest.

Pill diary: When the participant is released from quarantine the electronic pill diary must be submitted electronically.

Monitoring co-inhabitants: Appropriately delegated and credentialed study team members (as example: Clinical Research Coordinator) will ask the participant about the status of co-inhabitants daily to 14 days after the quarantine is completed to determine if the participant's co-inhabitants did or did not have symptoms or tested positive for COVID-19.

8.4.2 Sub-Study 3:

SARS-CoV-2 testing: Hospital workers will be tested for SARS-CoV-2 virus by RT-PCR every month. This will be a nasopharyngeal swab that will be processed by Quest diagnostics performed during enrollment at one month and two months. This screening NP swab will provide results in EPIC for clinical action within 72 hours. Eligibility criteria to start study medication does not require a negative PCR result to return.

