10.2 Response Criteria

Sub-Study 1: Time to release from quarantine. The criterion is afebrile for 72 hours AND improvement of symptoms AND at least 7 or 10 days have passed since symptoms started (according to contemporary CDC guidelines). To quantitatively assess improvement of symptoms the grading system in Section 8.5 will be used.

The PATCH Trial

May 2020. There was a change in CDC guidelines on quarantine time following onset of symptoms, changing from 7 to 10 days. We have adopted the new guidelines, but some of the earlier patients enrolled in the study were released in a shorter time than they would have been under the new guidelines. Because the response is time to release, we will record both release dates for each patient. While the release based on 10 days will be the primary outcome, we will run a parallel analysis of the 7-day measure as part of a sensitivity analysis.

Sub-Study 3: Measurement of SARS-CoV-2 positivity defined by PCR. Time to infection will be defined as the time in days from enrollment on the study to time to COVID-19 symptoms.

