10.3 Off treatment/Off Study

Each participant has the right to withdraw from the study at any time without prejudice. The investigator may discontinue any person's participation for any reason, including adverse event or failure to comply with the protocol. Should a participant withdraw from the study, the reason(s) must be stated on the case report form, and a final evaluation of the participant should be performed. Reasons for withdrawal include the following:

Progression of Disease: Remove participant from protocol therapy at the time progressive disease is documented. Progression of disease is left to the discretion of the treating physician/ sub-Investigator; however, the following guidelines are provided to help decision making for discontinuing study drug:

Sub-study 1: Progression of disease can be confirmed if there is increase in COVID-19 symptom score for 2 days in a row and is three points higher than baseline. Once criteria for release from quarantine is met in SS1 the patient is off study. Once the person is hospitalized for COVID-19 in sub-study 1 the subject is off study. Participants who have progressive symptoms and are subsequently hospitalized as related to COVID-19 will not be crossed over to receive HCQ at the time of unblinding.

Sub-study 3: Development of new symptomology consistent with COVID-19: e.g. fever, cough, shortness of breath and SARS-COV2 test positivity would lead to unblinding. If on placebo the subject can crossover to HCQ for treatment and stay on study for 14 days or release from quarantine. If the subject was on HCQ the subject is off study and will be instructed to seek medical attention through their primary care physician

Extraordinary Medical Circumstance: If at any time the treating physician feels constraints of this protocol are detrimental to the participant's health remove the participant from protocol therapy.

Participant's refusal to continue treatment: In this event, document the reason(s) for withdrawal.

Failure to comply with protocol (as judged by the investigator such as compliance below 80%, failure to maintain appointments, etc.).

Withdrawal from treatment per patient choice: Patients may withdraw from study treatment at any point in the study for any reason. These subjects are allowed to withdraw from treatment but continue to participate with any of the other study procedures for the intended 2 month period.

Delay in treatment > 7 days due to toxicity

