In addition, at our second interim analysis for SS3, we will evaluate the conditional power based on our original assumptions. The actual effect size for this study is completely unknown. If the effect size is smaller than we anticipated but still promising, and our conditional power falls between 0.5 and 0.8, we will consider formally adjusting the sample size in SS3 to achieve a conditional power of 0.8 based on an updated understanding of the effect size (29).

Z-Value Boundaries			
	Boundaries		Information
Stage	Efficacy	Futility	Proportion
1	2.9473	-1.2318	0.2500
2	2.5825	-0.2676	0.5000
3	1.6664	1.6664	1.0000

P-Value Boundaries			
	Boundaries		Information
Stage	Efficacy	Futility	Proportion
1	0.00160	0.89099	0.2500
2	0.00491	0.60550	0.5000
3	0.04782	0.04782	1.0000

12.2 Analysis of Secondary Endpoints.

Secondary outcomes will at least be analyzed as summary statistics, with group means, odds-ratios, and 95% CIs. We may conduct exploratory analyses using regression methods appropriate for each type of measure.

Sub-Study 1: Rate of secondary infection of housemates is a binomial count by household. We will summarize the proportion or rate by group, with 95% CI. With sufficient data, we will explore subgroups, patient, and secondary patient characteristics using logistic regression. Rate of hospitalization is a binary measure. We will summarize rates by group, and estimate the odds-ratio for treatment. Adverse event rates will be summarized as a count by subject, and mean count by group, and we will estimate a rate-ratio for treatment.

Sub-Study 3: For hospital employees, Adverse event rates will be summarized as a count by subject, and mean count by group, and we will estimate a rate-ratio for treatment.

REFERENCES

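### In Sub-Study 1, housemates are observed until 14 days after each patient's own release, so the window depends on the primary outcome; Section 10.3 and Table 4 do not fit those calls

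*Protocol*

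**What the plan says.** The first-listed secondary objective of Sub-Study 1 is "Rate of participant-reported secondary infection of housemates" (Protocol, 1.2 Secondary Objectives).

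- **Follow-up of housemates.** Section 8.4.1, under monitoring of co-inhabitants, says study staff "will ask the participant about the status of co-inhabitants daily to 14 days after the quarantine is completed". They record whether housemates had symptoms or tested positive. No start day is given.
- **What ends quarantine.** Section 10.2 gives the response as "Sub-Study 1: Time to release from quarantine", reached when the fever, symptom and elapsed-time criteria are all met. Section 2.1 sets the clock: "The first date of quarantine will be considered the date of SARS-CoV-2 nasopharyngeal swab test that confirmed positivity".
- **Off-study rules.** Section 10.3 says "Once criteria for release from quarantine is met in SS1 the patient is off study", and then "Once the person is hospitalized for COVID-19 in sub-study 1 the subject is off study".
- **Schedule.** Table 4 in Section 9.0 has no housemate row, and its last column is the day of release.
- **Analysis.** Section 12.2 (printed inside Section 13) says "Rate of secondary infection of housemates is a binomial count by household", and continues: "We will summarize the proportion or rate by group, with 95% CI". It defines no common window, person-time denominator or censoring rule. The SAP covers Sub-Study 3 only.

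**The concern.** The secondary endpoint is counted over a period whose end is set by the primary outcome. If HCQ brings release forward, as the trial hopes, HCQ households are watched for fewer days than placebo households. Fewer housemate events could then be recorded on HCQ even if the risk to housemates were the same. A summary by arm could not separate less transmission from less observation. The distortion would appear exactly when the primary result is positive, which is when the housemate result would be cited in support.

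There is also a conflict of text. Section 8.4.1 needs contact for two weeks after release, Section 10.3 takes the patient off study on that day, and the schedule shows nothing after it. For a patient hospitalised before release, 8.4.1 gives no clear end date for the calls and 10.3 takes the patient off study. Staff cannot follow all three sections as written, and different readings would give different data.

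**Working it through.** **Inputs from the Protocol.** Median time to release is 14 days on placebo and 7 on HCQ, counted from the positive test; there are 100 patients, 1:1, with one-sided alpha 0.05 and stated power 93% (Section 13.1). The tail is 14 days (8.4.1). The current criterion requires 10 days from symptom onset (10.2), and onset is at most 4 days before testing (3.1.3).

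**Assumptions.** The documents give no household infection rate, so a range is used. Windows are counted from the positive test.

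**Step 1: the plan's own figure.** The plan states no figure for housemates. The 93% power carries the release-time assumption used here. With hazard ratio 0.5 and d events, power ≈ Φ(√(d/4) × ln 2 − 1.645). At d = 82 this is Φ(3.138 − 1.645) = 93.2%, and a group-sequential simulation with the stated boundaries gives 93.0%. The medians of 14 and 7 are therefore consistent with the plan's power.

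**Step 2: median windows under 8.4.1.** Placebo 14 + 14 = 28 days; HCQ 7 + 14 = 21 days.

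**Step 3: constant daily risk, equal in both arms.** If the 28-day risk is r, the 21-day risk is 1 − (1 − r)^(21/28).

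| Assumed 28-day risk (placebo) | 21-day risk (HCQ) | Ratio |
|---|---|---|
| 10% | 7.6% | 0.76 |
| 20% | 15.4% | 0.77 |
| 30% | 23.5% | 0.78 |

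The spurious relative reduction is about 22-24%. As a sensitivity check, let release times be exponential with rate λ = ln 2/median, and let the household hazard be h per day. The risk is then 1 − e^(−14h) × λ/(λ + h). At h = 0.005 this gives 15.3% against 11.2%, a ratio of 0.73. For h from 0.001 to 0.02 the ratio runs from 0.71 to 0.80. If release cannot occur before day 6, it runs from 0.69 to 0.77.

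**Step 4: risk that declines from the index test.** Let the hazard fall exponentially with mean m days, and let F(t) = 1 − e^(−t/m). The 21-day risk is 1 − (1 − r)^(F(21)/F(28)). For m = 14, F(21)/F(28) = 0.7769/0.8647 = 0.898. Results for r = 10% to 30%:

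| Mean m (days) | Ratio HCQ/placebo |
|---|---|
| 5 | 0.99 |
| 7 | 0.97 |
| 10 | 0.94 |
| 14 | 0.90-0.91 |

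The spurious reduction is about 1-10%.

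**Step 5: no difference in release times.** The windows then have the same distribution in both arms, and this source gives no bias.

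**Step 6: a common window.** If every household is observed to the same day, a risk unrelated to treatment gives the same expected proportion in both arms. At h = 0.005 over 28 days this is 1 − e^(−0.14) = 13.1% in each.

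**Step 7: what a bare 28-day cut-off would lose.** With exponential release, the share still in quarantine at day 28 is 0.5^(28/14) = 25% on placebo and 0.5^(28/7) = 6% on HCQ. The share with less than 14 days of follow-up after release is 0.5^(14/14) = 50% and 0.5^(14/7) = 25%. A fixed window should therefore not replace the 14-day tail.

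**The case against.** The strongest defence is that the endpoint means spread from the index patient. A tail of equal length after quarantine then covers late exposure equally in both arms. Release needs 10 days from onset, and onset is at most 4 days before testing, so release cannot precede about day 6 and every household is covered to about day 20. Only later events can differ. This stands, and it is why the effect may be as small as 1%. It does not remove the point: 8.4.1 records any housemate symptoms or positive test without attributing them to the patient, so background illness accrues with each day watched.

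A reader might infer that Section 10.3 ends housemate follow-up at release. The median windows would then be 14 and 7 days, and the ratio 0.50 to 0.58 under constant risk. The documents do not support that as fact. Section 10.3 never mentions co-inhabitants and sits among reasons for withdrawal and removal from protocol therapy. Section 8.4.1 is specific and expressly covers the period after quarantine. What can be said is that the sections conflict. Nor does 10.3 say that data from the households of hospitalised patients are discarded.

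A reader might also take 12.2 to exclude any allowance for time. It does not, since it permits a proportion or a rate; it only leaves the denominator undefined. The analysis is descriptive, with no test or power attached.

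Finally, the registration list in Section 4.3 refers to a quarantine of 14 days. If that were fixed, the window would be a constant 28 days, but it does not fit release by criteria and is one more wording to align.

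**Conclusion.** The point holds. The housemate window depends on the primary outcome and no common window is stated, so unequal observation would favour HCQ if HCQ shortens quarantine. At the plan's median windows the size is about 22-24% under constant risk, as for background infection, and about 1-10% if risk declines from the index test with a mean of 5 to 14 days. It is nil if release times are equal. The risk shapes and household rates are assumptions. The 22-24% should not be quoted as the expected bias, because it needs a risk unrelated to the patient's recovery.

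The conflict between 8.4.1 and 10.3, and the missing row in Table 4, do not depend on these assumptions and must be reconciled. The matter is confined to a secondary endpoint of Sub-Study 1. Its primary outcome and all of Sub-Study 3 are unaffected. Label: cheap improvement.

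**What to change.** The Protocol's introduction says Sub-Study 1 is still enrolling, so the wording can be changed.

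- **10.3:** state that being off study at release or hospitalisation does not end housemate follow-up. Leave the treatment rules as they are.
- **8.4.1:** state the day on which housemate questions begin. Continue calls to the later of 14 days after release and a common day from randomisation, for example day 28.
- **Table 4:** add a housemate row that extends past release.
- **12.2:** compare arms on housemate infection by the common day, and report the count to 14 days after release as a supporting summary.

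The cost is some wording, one table row, and about a week more of brief questions for patients released early. The common-day comparison omits late infections from long quarantines, which would be mostly on placebo if HCQ works. The supporting summary shows those.

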3.1.2 Competent and capable to sign informed consent

3.1.3 Subjects meeting the following criteria by arm:

3.1.3 Sub-Study 1:

- Age ≥40 years since the risk of prolonged disease that progresses to severe COVID-19 disease increases with age.
- PCR-positive for the SARS-CoV2 virus
- Fever or cough or shortness of breath
- ≤4 days since the first symptoms of COVID-19 and date of testing
- Not requiring hospitalization and is sent home for quarantine.
- Not taking azithromycin at the time of enrollment
- Symptomatic at the time of enrollment
- Must live within 30 miles of HUP or Penn Presbyterian Medical Center to facilitate drop-off of medication
- Must have access to a working computer, or smartphone and have internet access
- Must be willing to fill out a daily symptom diary
- Must be available for a daily phone call,
- Must take their own temperature twice a day
- Must be willing to report the observed symptoms and development of COVID-19 in the co-inhabitants of the residence at which the quarantine will be served.

Sub-Study 3 Health Care Worker Prevention

- Healthcare worker at HUP or PPMC (Healthcare worker is defined as: a UPHS employee that physically interact with COVID-19 patients e.g., doctors, nurses, respiratory techs, certified nursing assistants, emergency room techs, OB ultrasound techs).
- ≥20 hours per week of clinical work scheduled in the coming 2 months during the COVID-19 pandemic
- No fever, cough, or shortness of breath in the past 2 weeks unless a SARS-CoV-2 test was performed for these symptoms and the result was negative prior to enrollment

The PATCH Trial

- 3.1.4 Sub-studies 1 and 3: Willing to report compliance with HCQ in the form of a diary
- 3.1.5 Sub-Studies 1 and 3: Participants are willing to collect oral fluid using a simple applicator that is provided, and freeze these samples.
- 3.1.6 Not pregnant and/or breastfeeding, as determined below:
Sub-Study 1 and 3: Not known to be pregnant or breast feeding as determined through self-report

[All participants] 3.1.7 Patients must be able to swallow and retain oral medication and must not have any clinically significant gastrointestinal abnormalities that may alter absorption such as, but not limited to malabsorption syndrome, major resection of the stomach or bowels, gastric bypass, lap banding.

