4.3 Required Registration information

- Patient's initials (first and last)
- Patient's Hospital ID and/or last 4 digits of Social Security number
- Patient past medical history
- Body mass Index
- Smoking status Current former
- Gender
- Birth date (mm/yyyy)
- Race
- Ethnicity
- Nine-digit ZIP code
- State of residence
- County of residence
- Cell phone number and alternate numbers
- Email address
- Sub-study 1: A description (not containing PHI) for all full time inhabitants at the residence where the participant will stay during the 14-day quarantine.

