5.0 RANDOMIZATION

After all applicable screening assessments have been performed, participants who have met all inclusion criteria and none of the exclusion criteria will be centrally, randomly allocated to one of the two groups in each sub-study. Randomization will be done using computer generated randomization numbers. Treatment **should start within 3 working days after randomization.** Once the order for study drug arrives at the

The PATCH Trial

pharmacy and the participant is randomized only the pharmacist is aware of the assignment of HCQ versus placebo in the double blind sub-studies (1 and 3).

Blinding: Sub-Study 1 and 3 will have a double-blind placebo controlled design.

Unblinding: Sub-Study1: If a participant progresses with symptoms of COVID-19 based on the assessment scale outlined below an appropriately delegated and credentialed study team member will review the case with a clinical investigator who will sign off on the need to un-blind the participant. If the participant was on placebo and continues to have symptoms, then he/she will be allowed to crossover to the HCQ dosing. The EM van will deliver the HCQ to the participant. If the patient was on HCQ then HCQ will be stopped and the patient will be asked to seek the advice of their primary care doctor or go to the emergency room if symptoms are becoming more worrisome. Participants who have progressive symptoms and are subsequently hospitalized due to COVID-19 will be unblinded but not be crossed over to receive HCQ at the time of unblinding.

Sub-Study 3: If the participant at any time has worsening symptoms consistent with new onset of COVID-19 disease a COVID-19 PCR test is performed. Antibody tests alone will not be used to make decisions for this study. If the PCR test is positive for SARS-CoV-2 an appropriately delegated and credentialed study team member will contact IDS and the pharmacist will indicate which arm the participant was assigned. If the participant was assigned to placebo and wishes to cross over to HCQ, IDS will provide HCQ at the same dose as the Sub-Study 3 HCQ arm and IDS will ship the HCQ to the participant. If the participant was assigned to HCQ then the participant will be advised to seek the advice of their personal physician or go to the emergency room if symptoms are becoming more worrisome.

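### Sub-Study 1's housemate-infection endpoint has no at-risk denominator and no onset window, so illness preceding the index patient's first dose can be counted and dilute the comparison

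*Protocol*

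**What the plan says.** The objective is listed in Protocol section 1.2 as "Rate of participant-reported secondary infection of housemates, rate of hospitalization, rate of treatment related adverse events". Four other places bear on it:

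- **Data collection (8.4.1, Monitoring co-inhabitants).** Staff ask the participant whether co-inhabitants "did or did not have symptoms or tested positive for COVID-19". The questioning runs "daily to 14 days after the quarantine is completed". An end is given, but no start tied to randomization or first dose.
- **Registration (4.3).** The baseline item is "A description (not containing PHI) for all full time inhabitants at the residence". Symptom or test status is not mentioned.
- **Eligibility (3.1.3, Sub-Study 1).** The participant "Must be willing to report the observed symptoms and development of COVID-19 in the co-inhabitants of the residence".
- **Analysis (12.2, Analysis of Secondary Endpoints).** "Rate of secondary infection of housemates is a binomial count by household", and "We will summarize the proportion or rate by group, with 95% CI". Exploratory logistic regression may follow.

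The Sub-Study 1 schedule of events (Table 4) has no row for co-inhabitants. The SAP covers Sub-Study 3 only.

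**The concern.** The scientific question is whether treating the index patient reduces onward spread in the home. That concerns only housemates who are uninfected when treatment starts. The protocol names no such group, asks for no onset date, and sets no time from which a case counts. An analyst working from sections 8.4.1 and 12.2 would have no stated ground for removing a housemate who was coughing on the day of the first dose.

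Cases that precede the drug add the same expected amount to both arms, which moves a risk ratio or odds ratio toward 1. A real effect on household transmission could then look weak or absent. Leaving the rule open also means that the choice of who counts could be made after the data are seen.

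**Working it through.** **Is there a figure to reproduce?** No. The documents give no household size, expected rate, sample size or power for this endpoint.

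**How much exposure can precede the first dose?** Section 3.1.3 allows up to 4 days from first symptoms to testing. Notification of the result, e-consent, and preparation and delivery of drug take further time that the protocol does not state. Section 5.0 says treatment "should start within 3 working days after randomization". The two stated maxima sum to 4 + 3 = 7 days, before adding the unstated steps or any weekend. These are upper limits; a patient tested on the day of onset and treated promptly would have far less. They show only that housemates infected by the index patient before dosing are a realistic group, so the word secondary does not by itself exclude them.

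**Does the trial handle this elsewhere?** Yes. In Sub-Study 3, participants who are PCR-positive at baseline are replaced and are not evaluable for the primary outcome (8.4.2 and 10.1). The housemate endpoint has no counterpart.

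**Illustration of the dilution.** Every rate here is an assumption. Let f be the share of housemates already ill at first dose (equal in both arms in expectation), q the placebo risk among the rest, and 0.50 the true risk ratio. Counted risks are

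p0 = f + (1 − f)q and p1 = f + (1 − f)q × 0.50.

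For f = 0.20 and q = 0.30: p0 = 0.20 + 0.80 × 0.30 = 0.44, p1 = 0.20 + 0.80 × 0.15 = 0.32, and p1/p0 = 0.73. The risk difference shrinks by the factor (1 − f), here from 0.15 to 0.12.

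The power columns assume 100 housemates per arm (two for each of 50 index patients), a two-sided 5% test of two proportions, and no clustering by household. The restricted column uses 100(1 − f) housemates per arm with risks q and 0.50q.

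| q | f | p0 | p1 | Counted RR | Power, all housemates | Power, restricted |
|---|---|---|---|---|---|---|
| 0.30 | 0.10 | 0.370 | 0.235 | 0.64 | 55% | 68% |
| 0.30 | 0.20 | 0.440 | 0.320 | 0.73 | 42% | 62% |
| 0.30 | 0.30 | 0.510 | 0.405 | 0.79 | 32% | 57% |
| 0.15 | 0.10 | 0.235 | 0.168 | 0.71 | 22% | 36% |
| 0.15 | 0.20 | 0.320 | 0.260 | 0.81 | 15% | 32% |
| 0.15 | 0.30 | 0.405 | 0.352 | 0.87 | 12% | 29% |

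In these cases the restriction gains more than the smaller denominator costs. The restricted column is a best case, because it assumes that every pre-dose case is recognised.

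**How much can a baseline question remove?** It finds only housemates who have symptoms or a known positive test. Let π be the share of counted placebo cases infected before first dose, so counted RR = π + (1 − π) × 0.50. If a share d of the pre-dose infections is detectable and excluded, the remaining share is π′ = π(1 − d)/[π(1 − d) + (1 − π)]. With π = 0.60 the unrestricted RR is 0.80. Then:

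- d = 0.25: π′ = 0.45/0.85 = 0.53, RR = 0.76
- d = 0.50: π′ = 0.30/0.70 = 0.43, RR = 0.71
- d = 0.75: π′ = 0.15/0.55 = 0.27, RR = 0.64

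The dilution is reduced, but the true 0.50 is not recovered.

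**The case against.** The strongest reply is that the protocol has no rule that counts housemates who were already ill. Section 8.4.1 describes what staff ask, not who is a case, and section 12.2 states no denominator. The endpoint's name and the eligibility wording both point to new disease. A reader might infer that a housemate who tested positive before the index patient enrolled is scored as a secondary infection, so that co-primary cases count. The documents do not support that. They are silent, and ordinary usage points the other way. This part of the objection stands, and the point is therefore an omission. It remains a point because a housemate infected by the index patient before first dose is secondary on any reading.

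A reader might also infer that most household transmission precedes the drug, or that the fix restores the true effect. The first needs a transmission curve and a distribution of times to first dose, and the protocol gives only upper limits on two intervals. The second fails on the residual calculation above; no provision is made for testing co-inhabitants, so incubating housemates would go unseen.

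Finally, daily questioning may allow onset to be reconstructed, and Sub-Study 1 is to be reported separately, so a later plan could settle the matter. That is fair in part. Reconstruction works only if the calls begin by the first dose and status is kept for each housemate, and the protocol requires neither.

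**Conclusion.** The point holds as a cheap improvement to a descriptive secondary endpoint. The at-risk group and the onset window are undefined, and pre-dose illness can enter the count. The direction is toward no effect. In expectation it creates no false difference between arms, given randomization, and it does not touch the Sub-Study 1 primary result.

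The size cannot be derived from the documents. The range of 0.64–0.87 for a true risk ratio of 0.50 rests on an assumed 10–30% of housemates already ill and 15–30% incident risk. The power figures further assume 100 housemates per arm and independence within households. Only the direction is independent of these values.

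**What to change.** 1. At the enrolment or first-dose call, record for each co-inhabitant the symptoms, test status and onset date.
2. Define the denominator as co-inhabitants with no symptoms and no positive test at the index patient's first dose.
3. Count as a secondary infection only new onset or a new positive test after that dose, keeping the protocol's existing symptom wording.
4. Report two sensitivity analyses: the count over all housemates, and a version that starts counting after a prespecified lag from first dose, to allow for housemates who were incubating.
5. State when the window closes. Section 10.3 takes the participant off study once release criteria are met, while section 8.4.1 continues the household questions for 14 days beyond quarantine; the two need reconciling.

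The cost is one added baseline field per co-inhabitant and a few sentences of endpoint definition; the daily questions already exist. The introduction to the protocol supplement says Sub-Study 1 is still enrolling, so the change can still be used, and it should be fixed before unblinded analysis. The downsides are a smaller denominator and only partial removal of the dilution, since undetected pre-dose infections remain.
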